9. DATA HANDLING AND RECORD KEEPING

9.1 Data Collection

Data will be collected during this clinical trial. Data will be captured on case report forms (CRF), initially this will be on paper forms. Once the electronic remote data capture (eRDC) systems is implemented sites will be informed and further details provided. The Case Report Form (paper CRF/eRDC) is listed in Table 6 below.

Form	Summary of data recorded	Schedule for submission
Eligibility Checklist	Confirmation of eligibility	Faxed at point of randomisation .
Randomisation	Patient details and trial Number	At point of randomisation
Dosing Forms		.
GSK1070806 / Placebo Dosing	Dose level, visit, date, dosing details	Within 2 weeks of dosing
Sample Analysis Forms		
Pharmacokinetics	Date, visit, sample collection, time taken	Within 2 weeks of visit
Pharmacodynamics	Date, visit, sample collection, time taken	Within 2 weeks of visit
Pharmacogenomics	Date, visit, sample collection, time taken	Within 2 weeks of visit
Additional Research	Date, visit, sample collection, time taken	Within 2 weeks of visit
Faecal Calprotectin	Date, visit, sample collection, time taken	Within 2 weeks of visit
Assessment Forms		
CDAI	Date, details of CDAI scoring	Within 2 weeks of visit
Endoscopy with Biopsy	Date, details of endoscopy and biopsies	Within 2 weeks of visit
Endoscopic Score for CD Form	Date, visit, details of SES-CD scoring and Rutgeerts Score if applicable	Within 2 weeks of visit
Laboratory	Date, visit, results, clinical significance	Within 2 weeks of visit
ECG	Date, visit, results, interpretation	Within 2 weeks of visit
Demographics	Date, visit, age, gender, ethnicity	Within 2 weeks of visit
Physical Examination	Date, visit, investigations, result	Within 2 weeks of visit
Vital Signs	Date, visit, time, results	Within 2 weeks of visit
Pregnancy Test	Date, visit, result	Within 2 weeks of visit
Clostridium Difficile Testing	Date, visit, results	Within 2 weeks of visit

Table 9 : Description of Case Report Forms

Form	Summary of data recorded	Schedule for submission	
Influenza Risk Screening	Date, visit, assessment, outcome	Within 2 weeks of visit	
Serology Screening	Date, visit, results	Within 2 weeks of visit	
T-SPOT TB Test	Date, visit, results	Within 2 weeks of visit	
Adverse Event	Start and stop dates, grade according to CTCAE version 4.0, causality	Within 2 weeks of each visit	
Concomitant Medication	List of concomitant medication	Within 2 weeks of each visit	
Ad Hoc Forms			
Treatment Discontinuation	Date, reasons	Immediately after discontinuation of treatment	
Serious Adverse Event	Date, details of the SAE	Within 24 hrs of being made aware of the SAE	
Liver Toxicity	Date, details of liver toxicity	Within 24 hours of liver toxicity event	
Pregnancy Notification	Date, patient details and details of pregnancy	Within 24 hrs of being made aware of the pregnancy	
Death	Date, cause of death	Immediately upon notification of death	
Deviation	Date, details of deviation I	Immediately upon discovering deviation.	
Withdrawal	Date, details of withdrawal	Immediately upon patient withdrawal	

The CRF must be completed, signed/dated (for paper CRFs only) and returned to the CDAID Trials Office by the Investigator or an authorised member of the site research team (as delegated on the Site Signature and Delegation Log) within the timeframe listed above entries on the CRF should be made in ballpoint pen, in blue or black ink, and must be legible. Any errors should be crossed out with a single stroke, the correction inserted and the change initialled and dated. If it is not obvious why a change has been made, an explanation should be written next to the change.

Data reported on each form should be consistent with the source data or the discrepancies should be explained. If information is not known, this must be clearly indicated on the form. All missing and ambiguous data will be queried. All sections are to be completed before returning.

Data provided on the Quality of Life Forms will not be captured on source data. This data will be written directly onto the CRF's.

In all cases it remains the responsibility of the Investigator to ensure that the CRF has been completed correctly and that the data are accurate.

The completed originals should be sent to the CDAID Trials Office and a copy filed in the ISF.

Trial forms may be amended by the CDAID Trials Office, as appropriate, throughout the duration of the trial. Whilst this will not constitute a protocol amendment, new versions of the form must be implemented by participating sites immediately on receipt.

9.2 Archiving

It is the responsibility of the Principal Investigator to ensure all essential trial documentation and source records (e.g. signed ICFs, ISFs, Pharmacy Files, patients' hospital notes, copies of CRFs etc.) at their site are securely retained for at least 25 years after the end of the trial or following the processing of all biological material collected for research, whichever is the later. Do not destroy any documents without prior approval from the CRCTU Archivist.

10. QUALITY MANAGEMENT

The CDAID clinical trial in patients with CD is being conducted under the auspices of the Cancer Research UK Clinical Trials Unit (CRCTU) according to the current guidelines for Good Clinical Practice (GCP). Participating sites will be monitored by CRCTU staff to confirm compliance with the protocol and the protection of patients' rights as detailed in the Declaration of Helsinki: October 1996 (Appendix 1).

10.1 Site Set-up and Initiation

All sites will be required to sign a Clinical Study Site Agreement prior to participation. In addition all participating Investigators will be asked to sign the necessary agreements, Investigator Registration Forms and supply a current CV and GCP to the CDAID Trials Office. All members of the site research team will also be required to sign the Site Signature and Delegation Log, which should be returned to the CDAID Trials Office. Prior to commencing recruitment all sites will undergo a process of initiation. Key members of the site research team will be required to attend either a meeting or a teleconference covering aspects of the trial design, protocol procedures, AE reporting, collection and reporting of data and record keeping. Sites will be provided with an ISF and a Pharmacy File containing essential documentation, instructions, and other documentation required for the conduct of the trial. The CDAID Trials Office must be informed immediately of any change in the site research team

10.2 On-site Monitoring

Monitoring will be carried out as required following a risk assessment and as documented in the CDAID Quality Management Plan. Additional on-site monitoring visits may be triggered for example by poor CRF return, poor data quality, low SAE reporting rates, excessive number of patient withdrawals or deviations. If a monitoring visit is required the Trials Office will contact the site to arrange a date for the proposed visit and will provide the site with written confirmation. Investigators will allow the CDAID trial staff access to source documents as requested.

10.3 Central Monitoring

Trials staff will be in regular contact with the site research team to check on progress and address any queries that they may have. Trials staff will check incoming CRFs for compliance with the protocol, data consistency, missing data and timing. Sites will be sent Data Clarification Forms (DCFs) requesting missing data or clarification of inconsistencies or discrepancies.

Sites may be suspended from further recruitment in the event of serious and persistent non-compliance with the protocol and/or GCP, and/or poor recruitment. Any major problems identified during monitoring may be reported to the Trial Management Group and the Trial Steering Committee and the relevant regulatory bodies. This includes reporting serious breaches of GCP and/or the trial protocol to the Research Ethics Committee (REC) and the Medicines for Healthcare products Regulatory Agency (MHRA).

CDAID

10.4 Recruitment Period

Recruitment in the CDAID trial is estimated to take place over an approximate 12-18 month period. Due to the total number of included patients being set at 21 in total, the maximum recruitment rate required per site will be approximately one /two patients per month. With an estimated 5 new referrals per week at each site, the perception is that this target will be met without difficulty.

10.5 Study Timelines (estimates)

First Patient First Visit (FPFV)	=	November 2018
First Patient First Treatment (FPFT)	=	December 2018
Last Patient Last Treatment (LPLT)	=	December 2019
Last Patient Last Visit (LPLV)	=	May 2020

10.6 Audit and Inspection

The Investigator will permit trial-related monitoring, audits, ethical review, and regulatory inspection(s) at their site, providing direct access to source data/documents.

Sites are also requested to notify the CDAID Trials Office of any MHRA inspections.

10.7 Notification of Serious Breaches

In accordance with Regulation 29A of the Medicines for Human Use (Clinical Trials) Regulations 2004 and its amendments, the Sponsor of the trial is responsible for notifying the licensing authority in writing of any serious breach of:

- The conditions and principles of GCP in connection with that trial or;
- The protocol relating to that trial, within 7 days of becoming aware of that breach

For the purposes of this regulation, a "serious breach" is a breach which is likely to effect to a significant degree:

- The safety or physical or mental integrity of the subjects of the trial; or
- The scientific value of the trial

Sites are therefore requested to notify the Trials Office of a suspected trial-related serious breach of GCP and/or the trial protocol. Where the Trials Office is investigating whether or not a serious breach has occurred sites are also requested to cooperate with the Trials Office in providing sufficient information to report the breach to the MHRA where required and in undertaking any corrective and/or preventive action.

11. END OF TRIAL DEFINITION

The end of trial will be the date of Last Patient Last Visit (LPLV). The CDAID Trials Office will notify the MHRA and REC that the trial has ended and will provide them with a summary of the clinical trial report within 12 months of the end of trial. Within the same timeframe a summary clinical trial report will also be provided to the funders of the project (GSK)

After closure of the trial with the MHRA, the Sponsor is no longer required to notify the MHRA and REC of changes of Principal Investigator. However, sites should continue to notify the CDAID Trials Office of changes in Principal Investigator by completing and returning (where required) an Investigator Registration Form together with a current signed and dated CV.

12. STATISTICAL CONSIDERATIONS

The proposed analysis methods are described in Section 12.2. Success of the trial with respect to CDAI score will be defined as concluding that the mean response profile under GSK1070806 is superior (i.e. takes lower values) to that under placebo. This repeated measures analysis will be performed using a regression model. The determination of success is not attached to any particular time-point, but considers outcomes at all times. Secondary outcome measures will provide supportive evidence for the effect of GSK1070806 in patients with active CD.

Up to 21 patients will be randomised to GSK1070806 or placebo in a 2:1 ratio. The sample size has been chosen based on feasibility and practical constraints. This trial was initially conceived using a sample size of at least 30 patients. An indication of the statistical performance of the trial with n=30 using the proposed analysis method is given in Section 12.3.

12.1 Definition of Outcome Measures

Outcome measures are defined in Section 2.

12.2 Analysis of Outcome Measures

12.2.1 Outcomes with Repeated Measures

Outcomes with repeated measures (i.e. those with at least two post-baseline measurements, such as CDAI) will be analysed by hierarchical models. Terms will be included to reflect the effects of assessment time, the interaction of treatment arm with assessment time, and baseline heterogeneity in patients. Inference on the effect of GSK1070806 with respect to an outcome measure will be made by assessing the necessity of the treatment arm variables in modelling the mean outcome paths by trial arm, i.e. investigating if the mean outcome paths diverge. Smooth functions of time will be used in the modelling where they can be justified by the data, but a fully-specified model with estimates of treatment effects in each arm at each time-point will be used if smooth functions are not appropriate. Further model features, such as specialised covariance structures will be considered as necessitated by the data. The estimated mean difference between treatment arms through time will be reported with appropriate estimates of variability. Demonstrations of the proposed analysis method with respect to CDAI are given in Section 12.3.1.

It is our intention to use a Bayesian implementation of the above method to compare CDAI outcomes (and other clinical efficacy outcomes) under GSK1070806 and placebo. We propose to use moderately informative priors on the expected outcomes of patients allocated to placebo. These will be justified using published studies where placebo was used and CDAI was assessed in patients with CD. Priors with mean zero will be used for the mean response to experimental drug in excess of placebo effect. This will allow us to preferentially randomise to the experimental therapy, whilst maintaining statistical performance in a manner consistent with published data.

CDAID

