12.3.1 Simulating CDAI paths for patients in a scenario

- 1) Baseline values of CDAI score for patients allocated to placebo and GSK1070806 are randomly sampled from a Normal (285, 80²) distribution. Thus, baseline CDAI scores are centred at 285 and 95% of values are in the approximate interval (125, 445).
- 2) Vectors of treatment-effects at weeks (0, 2, 4, 8, 12, 16, 24) are selected for placebo, $\lambda_P(t)$, and GSK1070806, $\lambda_E(t)$. These reflect the value of the mean CDAI path through time as a multiple of the baseline value. Values less then 1 show improvement, i.e. falling CDAI scores. The chosen subscripts are *P* for placebo and *E* for experimental treatment.
- 3) The value at time t of the CDAI path for a patient with baseline score y_0 allocated to treatment A is

$$y_0 * \lambda_A(t) + \epsilon$$

where ε is a noise term, distributed N(0, 30²). For instance, if a patient has y₀ = 300, is allocated to GSK1070806 with $\lambda_{E}(t) = 0.9$, and happens to take $\varepsilon = 12$ at time *t*, then for that patient:

CDAID

The mean baseline value and variability of baseline scores were selected to mimic those reported in a recentlypublished randomised controlled trial (RCT) of CD: (Zhang, Lv et al. 2018). Under the described method, the variability of CDAI scores are driven by the variability of the baseline scores and the noise terms. The variance of the noise, 302, was chosen by trial-and-error so that the overall variability of the CDAI scores approximately matched those at the time horizons reported in [Zhang et al. 2017].

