12.3.2 Reaching a trial decision in simulations

In simulations, we analyse outcomes using the model

$$y_{ij} = \alpha + a_i + \beta_j + \gamma_j z_i + \epsilon_{ij}$$

where:

- y_{ij} is the CDAI value of patient *i* at time t_{j} ;
- *α* is the mean baseline CDAI value across both arms;
- a_i is the random effect for the baseline CDAI score for patient *i*;
- β_i is the fixed placebo effect at time t_i ;
- γ_i is the fixed effect of the experimental drug over placebo at time t_i ;
- z_i takes the value 1 for patients allocated to GSK1070806, else 0;
- ϵ_{ij} is the noise time for patient *i* at time t_{j} ;
- $a_i \sim N(0, \sigma_a^2)$
- $\epsilon_{ii} \sim N(0, \sigma^2)$

The presence of a treatment effect is formally tested by the hypothesis:

$$\gamma_1 = \gamma_2 = \dots = \gamma_j = 0$$

The presence of aggregate treatment benefit is tested via the supplemental requirement that:

$$\sum_j \gamma_j < 0$$

We present in the following sections the performance of these combined criteria, fitting mixed effects models by REML using the nlme package in R, interpreting p-values less than 0.05 as being significant.

It should be noted that the analysis method in this section does not reflect exactly our proposal for the trial. As noted above, we propose to use the Bayesian analogue to this method with informative priors on the placebo effects. This extra information should increase the ability of the model to distinguish between the paths by arm, without unduly increasing the false positive rate. Furthermore, we would hope to model the CDAI paths using smooth functions of time (for instance, polynomials). These would require fewer parameters than the saturated model above. This would hopefully improve statistical performance as well.

12.3.3 Scenario 1

In this null scenario, we assume that the placebo effect is positive but very small, and that GSK1070806 is assumed to have no effect on CDAI beyond placebo effect. The values of $\lambda P(t)$ and $\lambda E(t)$ are identical, given in column A of Table 10. The expected change from baseline is shown in column G. A single trial simulation using n1 = 10 placebo paths and n2 = 20 experimental paths is shown in Figure 4. We see that the mean lines are colocated and the confidence intervals largely overlap. This is the null scenario. The probability of approving GSK1070806 in this scenario is approximately 3.1%.

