12.3.8 Summary

This section summarises the simulated information presented in the preceding sections.

Table 10 Columns A-D show the scalars, $\lambda(t)$, applied to baseline CDAI values to generate post-baseline values.

The mean CDAI score at baseline for patients allocated to placebo and GSK1070806 alike is 285. Change in mean CDAI path is calculated by scaling this baseline mean by the relevant scalar, e.g. 285 * 0.99 – 285 = -3 and 285 * 0.95 – 285 = -14 (0 d.p.).

Colum n	A	В	С	D	E	F	G	н	1	J	к	L
	Scalar of mean CDAI path						Change in mean CDAI path vs baseline					
Time (weeks)	Placebo in Scen 1-4; & GSK107080 6 in Scen 1	GSK107080 6 in Scen 2	GSK107080 6 in Scen 3	GSK107080 6 in Scen 4	Placeb o in Scen 5	GSK107080 6 in Scen 5	Placebo in Scen 1-4; & GSK107080 6 in Scen 1	GSK107080 6 in Scen 2	GSK107080 6 in Scen 3	GSK107080 6 in Scen 4	Placeb o in Scen 5	GSK107080 6 in Scen 5
0	1.00	1.00	1.00	1.00	1.00	1.00	0	0	0	0	0	0
2	0.99	0.95	0.97	0.96	0.97	0.90	-3	-14	-9	-11	-9	-28
4	0.99	0.90	0.95	0.92	0.94	0.82	-3	-28	-14	-23	-17	-51
8	0.98	0.80	0.89	0.86	0.89	0.75	-6	-57	-31	-40	-31	-71
12	0.98	0.78	0.83	0.81	0.85	0.70	-6	-63	-48	-54	-43	-86
16	0.98	0.78	0.78	0.81	0.85	0.68	-6	-63	-63	-54	-43	-91
24	0.98	0.78	0.78	0.81	0.85	0.66	-6	-63	-63	-54	-43	-97
Prob (Approve)	0.031	0.928	0.860	0.851		0.880						

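### Section 12.3.2 words the CDAI model with one baseline mean for both arms, but Table 10 fits only a model with a free week-0 arm term; at n=21 the choice is worth about 12 to 18 points of success under the protocol's own simulation

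*Protocol*

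**What the plan says.** Section 12.2.1 plans hierarchical models for repeated outcomes: "Terms will be included to reflect the effects of assessment time, the interaction of treatment arm with assessment time, and baseline heterogeneity in patients". It mentions neither a common baseline mean nor a baseline covariate, and it points to the simulation section for a demonstration on CDAI.

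Section 12.3.2 writes the simulated model as an intercept, a patient random effect, a time effect, a drug effect gamma at each time, and noise. The intercept "is the mean baseline CDAI value across both arms". All gammas are tested jointly, "interpreting p-values less than 0.05 as being significant". A second condition concerns direction: "The presence of aggregate treatment benefit is tested via the supplemental requirement that" the gammas sum to less than zero. The section adds that the trial itself will use a Bayesian analogue with informative priors on the placebo effects.

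The data recipe in 12.3.1 includes week 0 among the times: "Vectors of treatment-effects at weeks (0, 2, 4, 8, 12, 16, 24) are selected". Nothing says whether gamma exists at week 0 or is fixed at zero there. Table 10 gives the approval probabilities at 10 placebo and 20 active patients. Section 12 sets the actual size at up to 21, randomised 2:1.

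**The concern.** Randomised arms have the same expected baseline, so a model with one baseline mean uses each patient's week-0 score to correct for chance imbalance. If the arms may also differ at week 0, that correction is lost. With complete data and a separate arm effect at every time, each gamma is simply the raw difference in arm means at that visit. A patient-level random intercept does not remove an imbalance between arm averages.

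The wording of the intercept suggests the first model, while the published probabilities behave like the second. A reader cannot tell which structure the key secondary analysis is meant to have. At 21 patients the difference matters, because the chance imbalance is about as large as the assumed drug effects.

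**Working it through.** **Inputs.** Baseline CDAI values "are randomly sampled from a Normal (285, 80²) distribution" and visit noise has SD 30 (12.3.1). Scalars come from Table 10, columns A to F. The fit is REML with a random intercept, p < 0.05 and sum of gammas < 0 (12.3.2). Arm sizes are 10:20 as simulated, and 7:14 for n=21.

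**Step 1: reproduce Table 10 at 10:20** (10,000 trials per scenario, approval in %).

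| Model | Sc 1 | Sc 2 | Sc 3 | Sc 4 | Sc 5 |
|---|---|---|---|---|---|
| Table 10 | 3.1 | 92.8 | 86.0 | 85.1 | 88.0 |
| Arm term free at week 0 | 2.9 | 92.9 | 86.0 | 85.3 | 88.6 |
| Common baseline mean | 3.0 | 99.9 | 99.5 | 97.8 | 96.2 |
| Post-baseline data only | 2.8 | 81.9 | 80.6 | 64.3 | 47.7 |

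Five model forms were tried, with and without noise on the week-0 value. For the free-arm model the sum was taken both over all seven gammas and over the six post-baseline ones. Only one combination matches all five figures: the free week-0 arm term, a joint 7-df test, a noise-free baseline, and the sum over the six post-baseline gammas.

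**Step 2: size of the imbalance.** The SD of the difference in baseline means is 80 × sqrt(1/n1 + 1/n2).
- 10:20: 80 × sqrt(1/10 + 1/20) = 31.0
- 7:14: 80 × sqrt(1/7 + 1/14) = 37.0

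The mean drug effect over the six post-baseline visits is 285 × (sum of placebo scalars − sum of active scalars)/6.
- Scenario 2: 285 × (5.90 − 4.99)/6 = 43.2
- Scenario 3: 285 × (5.90 − 5.20)/6 = 33.3
- Scenario 4: 285 × (5.90 − 5.17)/6 = 34.7
- Scenario 5: 285 × (5.35 − 4.51)/6 = 39.9

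**Step 3: chance that the sum has the wrong sign, arm term free.** Let S_E and S_P be the active and placebo scalar sums. The sum of the six raw differences has mean 285(S_E − S_P) and variance 6400(S_E²/n2 + S_P²/n1) + 6 × 900(1/n1 + 1/n2). For Scenario 3 at 7:14:
- mean = 285 × (−0.70) = −199.5
- variance = 6400(27.04/14 + 34.81/7) + 5400 × 0.2143 = 45,345, so SD = 212.9
- P(sum < 0) = Φ(199.5/212.9) = 0.826

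The wrong-sign probability is therefore 17.4%. The same formula gives 10.9, 16.4 and 10.5% in Scenarios 2, 4 and 5. Simulation agrees (10 to 17%). With a common baseline mean it is about 0%.

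**Step 4: success at 7:14** (30,000 trials per scenario, %; gains taken before rounding).

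| | Sc 1 | Sc 2 | Sc 3 | Sc 4 | Sc 5 |
|---|---|---|---|---|---|
| Arm term free at week 0 | 3.2 | 85.3 | 76.5 | 69.7 | 67.4 |
| Common baseline mean | 3.3 | 97.2 | 94.5 | 86.1 | 79.3 |
| Gain | 0.1 | 11.8 | 18.0 | 16.4 | 11.9 |

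**Step 5: sensitivity.** If the week-0 score also carries SD-30 noise, success (10,000 trials) goes from 80.5/72.4/62.8/56.6% to 91.2/88.4/76.6/66.5%, a gain of about 10 to 16 points. As an assumption outside the protocol, SD 60 at every visit cuts the gain to single digits (about 1 to 9 points in a run of 1,200 trials per scenario).

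**The case against.** The written model can fairly be read as already having a common baseline: the intercept spans both arms, and no sentence says that a week-0 arm term is fitted. The free term is inferred from which model returns Table 10, and the matching combination is an odd one, since week 0 is in the joint test but not in the sum. This stands, and it is why the point is a mismatch between text and table and not proof of what the trial will do.

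A reader might infer that the trial's success will be decided by the sum rule and that its real power is 12 to 18 points too low. The documents do not support that. Section 12.3.2 says its method is not exactly the trial's. Section 12 defines success as a superior mean profile, without a sum rule. The planned Bayesian version adds priors and possibly smooth curves. It is described as an analogue of this model, so it inherits the open question about week 0, but the size of the effect there is unknown.

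A reader might also infer bias or a raised false-positive rate. Neither follows: the null rate is about 3% both ways, and imbalance averages out over randomisations.

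Details of baseline handling may sit in an analysis plan that is not at hand, and their absence from 12.2.1 alone would be no fault. Nor is the ANCOVA in 12.2.2 evidence of a contrary choice for CDAI, because it is offered only as a fallback where the hierarchical model is unsuitable. What no separate plan can settle is that 12.3.2 and Table 10 disagree within the protocol.

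**Conclusion.** The concern holds in this form. The model as worded does not produce the stated probabilities. The model that does produce them leaves chance baseline imbalance in the treatment contrasts.

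At n=21 that costs about 12 to 18 points of success and gives a wrong-signed sum in about 10 to 18% of active-drug trials. The common mean more than offsets the fall from 30 to 21 patients in Scenarios 2 to 4. In Scenario 5 it recovers about 56% of it: 11.9 of 88.6 − 67.4 = 21.2 points.

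These figures rest on the protocol's generator (follow-up proportional to an exact baseline, SD-30 noise), complete data, a 7:14 split and the illustrative REML rule. They shrink as visit noise grows.

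Severity is should-fix: CDAI is the key secondary outcome, safety is primary, and the sample size was set by feasibility.

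**What to change.** In 12.2.1 and 12.3.2 state one of two analyses:
- baseline is a response with one mean for both arms and no week-0 treatment term; or
- baseline CDAI is a covariate in a model of post-baseline scores only.

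These are not equivalent. Under the protocol's generator at n=21 the covariate model succeeds in about 100% of trials in Scenarios 2 to 5, against about 79 to 97% for the common mean. That near-certainty reflects a simulated baseline that predicts follow-up almost perfectly, and should not be taken as expected performance. Choose one.

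Then define aggregate benefit on the baseline-adjusted post-baseline contrasts, carry the choice into the Bayesian model, and re-run Table 10 with the chosen model, saying whether the simulated week-0 score carries noise.

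The cost is a few sentences and a simulation re-run. Baseline CDAI is already collected before dosing, so no visit or measurement is added.
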